#### **10.5.3 Health-related Quality of Life (HQOL)**

The SF-36 will be employed to assess HQOL in study subjects at Day 7, 28, Month 6, 12 and 24 post-operation. The mean scores of SF-36 will be summarized by visits according to treatment group. The change from baseline in the summary scores will be compared using an ANOVA with treatment as a factor. If the assumptions of the model are not met, the analysis will be done using Kruskal-Wallis tests.

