### **3.2 Secondary objectives**

The key secondary objective is to compare renal function of the everolimus treatment arms to the MMF/MPA treatment arm at 12 and 24 months post-transplantation. Renal function will be measured by the calculated glomerular filtration rate (GFR), using the MDRD (Modification of Diet in Renal Disease) formula (20).

Other secondary objectives include:

- The incidence of treated BPAR at 12 months
- The incidence of graft loss at 12 months
- The incidence of death or loss to follow up at 12 months
- Incidence of adverse events (AEs)
- Incidence of serious adverse events (SAEs)
- Incidence of new onset diabetes mellitus defined as non-diabetic patients before transplantation, who are receiving glucose lowering treatment for more than 30 days

post-transplant, or with a random plasma glucose  $\geq 200$  mg/dL (11.1 mmol/L) with 2 fasting plasma glucose values  $\geq 126$  mg/dL (7 mmol/L).

- Incidence of CMV (viremia or viruria) and BKV (viremia or viruria)
- Incidence of proteinuria by more than 3 fold or proteinuria reaching 1.5gm/day
- The comparison of the health related quality of life for patients treated with everolimus plus low dose tacrolimus to CellCept plus standard dose tacrolimus

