### 6.2 Treatment Arms

Within 24 hours after transplantation, after having met all inclusion/exclusion criteria, patients will be randomized to one of the following treatment groups in a ratio of 1:1:1. All patients will receive Campath or Simulect as induction therapy as well as Solumedrol infusion.

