### **7.6.2 Health-related Quality of Life**

The SF-36 is a widely used instrument to measure generic health status. It is a 36-item questionnaire that yields an 8-scale health profile as well as summary measures of individual patients. It has proven useful in monitoring generic and specific populations, comparing the relative burden of different diseases, differentiating the health benefits produced by different treatments, and in screening individual patients. The purpose collecting SF-36 data in this study is to compare the final health status of those on the ERL and low dose TAC arm of the trial to those on the ERL and low dose TAC which converts to MMF/MPA arm and to those on the MMF/MPA and standard dose TAC arm of the trial.

The eight profiles (scales) are: bodily pain, general health, vitality, mental health, physical functioning, role-physical, role-emotional and social functioning. The two summary measures are physical health and mental health.

Patients must complete the questionnaire before other clinical assessments at any given visit. The SF-36 can be administered in 5 to 10 minutes with a high degree of acceptability and quality. An appropriate person should be designated to facilitate self-administration. The administrator should not influence but can answer questions and address concerns and ensure that the questionnaire is filled out correctly and completely.

Completed questionnaires will be reviewed and examined by the investigator before the clinical examination for responses which may indicate potential AEs or SAEs. The

investigator should review not only the responses to the questions in the questionnaires but also for any unsolicited comments written by the patient.

If the occurrence of AEs or SAEs is confirmed, the physician must record the events as per instructions given in Section 7.5.1 of the protocol. Investigators should not encourage the patients to change the responses reported.

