## **10.5 Analysis of secondary objectives**

### **10.5.1 Efficacy (secondary)**

Secondary efficacy variables include:

- The incidence of treated BPAR at 24 months
- The incidence of graft loss at 24 months
- The incidence of death or loss to follow-up at 24 months

The incidence of treated BPAR, graft loss, and death or loss to follow-up will be analyzed using a Cochran-Mantel-Haenszel test stratified by induction therapy.

A Kaplan-Meier survival analysis will be performed for each time to treated BPAR, time to graft loss and time to death or loss to follow-up. The incidences will be compared among the three treatment groups using Kaplan-Meier probability estimates of efficacy failure and the associated 95 % CI obtained using the standard error derived by applying Greenwood's formula. The differences between the curves will be tested using the log-rank test.

FAS will be used for analyses of the secondary efficacy variables.

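### The SF-36 analysis in 10.5.3 is only an overall three-arm test; it names no between-arm contrast, so it answers neither statement of the quality-of-life objective

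*Combined protocol and SAP*

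**What the plan says.** The trial has three arms: "patients will be randomized to one of the following treatment groups in a ratio of 1:1:1" (6.2).

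The SF-36 aim appears in two places.

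- Section 3.2 lists, among the other secondary objectives, "The comparison of the health related quality of life for patients treated with everolimus plus low dose tacrolimus to CellCept plus standard dose tacrolimus". It names two regimens, gives no arm numbers and does not mention conversion.
- Section 7.6.2 gives the purpose of collecting the SF-36 as "to compare the final health status of those on the ERL and low dose TAC arm of the trial" first "to those on the ERL and low dose TAC which converts to MMF/MPA arm" and then to the MMF/MPA arm on standard-dose tacrolimus. Both comparisons start from Arm 1.

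Section 10.5.3 summarizes mean scores by visit and treatment group, then gives the test: "The change from baseline in the summary scores will be compared using an ANOVA with treatment as a factor". The fallback is: "If the assumptions of the model are not met, the analysis will be done using Kruskal-Wallis tests". It names no contrast, between-arm difference, confidence interval or multiplicity rule.

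**The concern.** With three arms, the null hypothesis of the ANOVA (and of Kruskal-Wallis) is that all three arms are the same. Both statements of the objective ask about particular pairs. A significant overall test does not say whether Arm 1 differs from Arm 3, from Arm 2, or from both. It can also be significant when Arm 1 and Arm 3 are identical and only the arm that stops tacrolimus differs. A non-significant result leaves the reader with group means but no planned estimate of the difference that the objective asks about. What is at stake is interpretation: a pilot is run largely to obtain estimates for planning, and this analysis yields a p-value that belongs to no pair.

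**Working it through.** **Inputs from the plan.** Three arms, 1:1:1 (6.2). 12 per group, 20% dropout, 16 per arm and 48 in total, effect size 0.9, two-sided alpha 0.05, block size 12 (10.6).

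**The plan's own sample size.** 12 / (1 − 0.20) = 15 per arm. Raising this to 16 gives 48 = 4 blocks of 12, so the figure reproduces. No power is stated for the SF-36. The 0.9 SD used below is the plan's general effect size, borrowed as an assumption.

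**Further assumptions.** Normal data with equal SD in every arm. The size of any Arm 2 shift is not in the documents, so a range is shown.

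**Case A: only Arm 2 differs, by d SD; Arm 1 equals Arm 3.** The means are (0, d, 0). The F-test noncentrality is λ = n × Σ(μᵢ − μ̄)² = n × (2/3)d².

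- n = 16, d = 0.9: λ = 16 × 0.54 = 8.64, with 2 and 45 df and critical F 3.20. The test rejects 72%.
- n = 12, d = 0.9: λ = 12 × 0.54 = 6.48, with 2 and 33 df and critical F 3.28. The test rejects 58%.

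| Arm 2 shift | ANOVA rejects, 16 per arm | ANOVA rejects, 12 per arm | Arm 1 vs Arm 3 contrast rejects |
|---|---|---|---|
| 0.5 SD | 27% | 21% | 5% |
| 0.9 SD | 72% | 58% | 5% |
| 1.0 SD | 81% | 67% | 5% |

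The last column is 5% by construction, because the two arms are equal. Simulated Kruskal-Wallis at 0.9 SD rejects about 69% (16 per arm) and 56% (12 per arm). In 67% of simulated trials at 0.9 SD and 16 per arm, the ANOVA was significant and the Arm 1 versus Arm 3 contrast was not.

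**Case B: Arm 1 differs from Arm 3 by 0.9 SD, 16 per arm.** The contrast uses the pooled error variance (45 df). Its noncentrality is 0.9 / √(2/16) = 0.9 × √8 = 2.55, against a critical t of 2.01.

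- Contrast at two-sided 0.05: power 70%.
- Contrast at the first Holm step for two tests (two-sided 0.025, critical t 2.32): power 59%.
- ANOVA with Arm 2 midway: λ = 16 × 0.9²/2 = 6.48, power 59%.
- ANOVA with Arm 2 equal to Arm 3: λ = 8.64, power 72%.

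So the contrast is more powerful than the overall test in one configuration and slightly less powerful in the other. The reason to prefer it is that its result belongs to a named pair.

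**The case against.** The strongest reply is that a three-group ANOVA is conventional for a three-arm trial and that the conversion arm is within the SF-36 aim. Much of this stands. Section 7.6.2 names Arm 2 as a comparator. The wording in 3.2 carries no arm number, the opening of 3.2 speaks of the everolimus arms in the plural, and section 4 describes both of those arms as everolimus with low-dose tacrolimus.

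A reader might therefore infer that the objective is strictly Arm 1 versus Arm 3, and that a rejection driven by Arm 2 is a false positive against it. The documents do not support that. On the 7.6.2 reading, a difference in Arm 2 is something the trial wants to know. The rejection rates in Case A are not inflated type I error either: the F test has the correct size for its own null, and nothing in the plan says that its p-value will be reported as an Arm 1 versus Arm 3 result.

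A reader might also carry the point over to 10.5.1, where "The incidences will be compared among the three treatment groups using Kaplan-Meier probability estimates of efficacy failure" and the curves are tested by log-rank. That does not follow. The component objectives in 3.2 (treated BPAR, graft loss, death or loss to follow-up) name no arms, so there is no stated pairwise objective for that test to contradict.

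Nor is it right that the plan gives no estimates at all, since group means by visit are summarized. What is missing is a named difference with its interval. That gap remains whichever section governs: even if all three arms are in scope, the overall test does not say which pair differs. Follow-up comparisons could be added after a significant F test, but none is specified.

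**Conclusion.** The point holds in a limited form. Sections 3.2 and 7.6.2 differ on which arms the SF-36 comparison covers, and 10.5.3 specifies no contrast that would answer either. The illustration is a 72% rejection rate at 16 per arm (58% at 12) with Arm 1 equal to Arm 3. It depends on an assumed Arm 2 shift of 0.9 SD, normal data and equal variances; at 0.5 SD the figures are 27% and 21%. It shows that the overall result cannot be attributed to a pair, not that the test is invalid. No general gain in power is claimed for contrasts. The severity is low: this is the last-listed secondary objective in a 48-patient pilot, with no SF-36 power claim.

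**What to change.** 1. Reconcile 3.2 with 7.6.2 so that both name the same arms by number.
2. In 10.5.3, make the main SF-36 analysis the contrasts that the reconciled objective names: Arm 1 versus Arm 3 and, as in 7.6.2, Arm 1 versus Arm 2. Estimate them from the same ANOVA with pooled variance, and report each as a difference with a 95% CI.
3. Apply Holm over the two contrasts if both are formally tested.
4. Replace the Kruskal-Wallis fallback with pairwise Wilcoxon tests for the same pairs.
5. Keep the overall p-value, if wanted, as descriptive.

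The cost is wording only, with no extra data or patients. Holm lowers contrast power at 0.9 SD and 16 per arm from about 70% to about 60%, and in some configurations the overall test would have been the more powerful. In return, the trial reports a difference with an interval that can be read against its own objective.

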#### **10.6 Sample size calculation**

Since this is a pilot study, the sample size estimation method proposed by Julious was considered in order to minimize the sample size (14). Julious proposes to employ sample size of 12 per group for a pilot study (14). Assuming the drop out rate of 20% along with the ease of blocked randomization, we propose the sample size of 16 per arm, totaling 48 patients. The estimated effect size,  $\alpha$ , and  $\beta$  corresponding to this sample size are 0.9, 0.05 (two-sided), and 0.2 respectively (15). A block size of 12 along with an allocation ratio of 1:1:1 will be employed as a randomization scheme.

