### Objectives:

- The primary objective of the study is to evaluate efficacy of Everolimus treatment arms compared to Mycophenolate treatment arm with respect to the composite efficacy failure rate including treated Biopsy-Proven Acute Rejection (BPAR) episodes, delayed graft function, graft loss, and death or loss to follow-up. The efficacy will be assessed at 6, 12 and 24 months in recipients of DCD and KDPI kidneys.
- Secondary: To compare renal function (glomerular filtration rate calculated using the MDRD formula) of everolimus with low dose tacrolimus regimen to that of MMF/MPA with standard dose tacrolimus regimen at 24 months post-transplant. Other secondary objectives are: to compare the incidence of CMV and BKV, new onset diabetes mellitus, chronic kidney disease with associated proteinuria, adverse events, serious adverse events and tacrolimus associated adverse events.

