### **Sample size justification:**

Since this is a pilot study, the sample size estimation method proposed by Julious was considered in order to minimize the sample size (14). Julious proposes to employ sample size of 12 per group for a pilot study (14). Assuming the drop out rate of 20% along with the ease of blocked randomization, we propose the sample size of 16 per arm, totaling 48 patients. The estimated effect size,  $\alpha$ , and  $\beta$  corresponding to this sample size are 0.9, 0.05 (two-sided), and 0.2 respectively (15). A block size of 12 along with an allocation ratio of 1:1:1 will be employed as a randomization scheme.

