## **Objectives:**

The primary objective of the study is to evaluate efficacy of Everolimus treatment arms compared to MMF/MPA treatment arm with respect to primary efficacy failure rate, namely, the composite efficacy endpoint, treated BPAR episodes, delayed graft function, graft loss, death or loss to follow-up, at 24 months in recipients of DCD or elevated KDPI kidneys.

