### **3.1 Primary objective**

The primary objective of this study is to evaluate concentration-controlled everolimus and low dose tacrolimus compared to MMF/MPA with standard dose tacrolimus at 24 months post-transplant with respect to the composite efficacy failure rates (treated biopsy proven acute rejection episodes (BPAR), graft loss, death, loss to follow-up) in *de novo* renal transplant recipients.

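### The only power statement (16 per arm, effect size 0.9, two-sided 0.05, 80%) names no endpoint, effect-size type or contrast, and as a two-arm mean comparison gives 69%; separately, the non-inferiority label has no margin or rule

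*Combined protocol and SAP*

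**What the plan says.** The sample size is built in two steps, in the same words in Section 10.6 and the synopsis. A published pilot-study proposal to "employ sample size of 12 per group for a pilot study" is combined with 20% dropout and convenience of blocking: "we propose the sample size of 16 per arm, totaling 48 patients". The plan then adds that effect size, alpha and beta "corresponding to this sample size are 0.9, 0.05 (two-sided), and 0.2 respectively", citing a textbook. Neither place gives an endpoint, an effect-size type or a contrast.

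Other sections do not supply them:

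- **Endpoint.** The primary variable in Section 10.4.1 is a binary composite. Section 10.4.2 assigns it an ANOVA; the synopsis and Section 10.7 use Fisher's exact test; Section 10.4.4 adds Cochran-Mantel-Haenszel and logistic regression as support. Section 10.7 is titled as power for secondary variables but contains no power figure. No SD or event rate appears in the plan.
- **Contrast, renal function.** Section 3.2 will "compare renal function of the everolimus treatment arms to the MMF/MPA treatment arm at 12 and 24 months post-transplantation". The synopsis compares "everolimus with low dose tacrolimus regimen to that of MMF/MPA with standard dose tacrolimus regimen at 24 months post-transplant".
- **Contrast, composite.** The Objectives paragraph in the Background will "evaluate efficacy of Everolimus treatment arms compared to MMF/MPA treatment arm with respect to primary efficacy failure rate", with arms in the plural. Section 3.1 will "evaluate concentration-controlled everolimus and low dose tacrolimus compared to MMF/MPA with standard dose tacrolimus at 24 months post-transplant", which reads as Arm 1 against Arm 3. Sections 10.4 and 10.5.1 compare three groups; Section 10.4.4 speaks of two.

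Section 4 describes the design as non-inferiority. No margin, non-inferiority hypothesis or confidence-limit rule follows anywhere.

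**The concern.** This sentence is the plan's only statement of power, and it cannot be tied to any planned analysis. A reader who meets a null result will use 0.9 SD and 80% to judge what the trial could have seen. If the figure belongs to a different test or contrast, that judgement will be too favourable. A reader may also carry it over to the primary composite, where it says nothing.

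The non-inferiority label raises a similar risk. The named tests (Fisher, chi-square, ANOVA, ANCOVA, Cochran-Mantel-Haenszel, log-rank, Wilcoxon, Kruskal-Wallis) are all tests of difference. Confidence intervals are reported in Section 10.4.4 but compared with no margin. A non-significant difference in a small trial could then be reported as non-inferiority.

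**Working it through.** **Inputs (Section 10.6):** 16 per arm, three arms, effect size 0.9, two-sided 0.05, beta 0.2, 12 per group from the pilot rule, 20% dropout, blocks of 12.

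**1. Headcount.** 12 / 0.8 = 15, raised to 16 so that 48 = 4 blocks of 12. This reproduces.

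**2. Two arms, unadjusted mean difference.** Noncentrality = d / sqrt(1/n1 + 1/n2) = 0.9 / sqrt(2/16) = 2.546. With 30 df the two-sided critical value is 2.042, and the noncentral t gives **69.3%**.

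- Normal approximation: Φ(2.546 − 1.960) = 72.1%.
- SD pooled over three arms (45 df): 70.2%.
- For 80%: 20 per arm gives 79.2% and 21 gives 81.2%.
- Difference detectable with 80% power: 1.02 SD at 16 per arm, 1.20 SD at 12.

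**3. One-sided 0.05, same comparison.** The critical value is 1.697 and power is **80.0%**. This matches the printed figures, but the text says two-sided.

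**4. Three-arm ANOVA F test, means spanning 0.9 SD.** λ = 48f², critical F(2, 45) = 3.204.

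- Middle arm halfway: f = 0.9 × sqrt(1/6) = 0.367, λ = 6.48, power 58.9%.
- Two arms equal: f = 0.9 × √2 / 3 = 0.424, λ = 8.64, power 72.2%.
- If 0.9 were itself Cohen's f: λ = 38.88 and power exceeds 99.9%, which does not correspond to beta 0.2 either.

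**5. Two-sided readings that come close to 80%.**

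- Everolimus arms pooled, 32 against 16: noncentrality 0.9 / sqrt(1/32 + 1/16) = 2.939, power 82.1%. With 24 against 12 evaluable it is 69.6%.
- ANCOVA, effective d = 0.9 / sqrt(1 − r²), 29 df: 80% needs r = 0.48 between Month 1 eGFR and the outcome. Section 10.5.2 names this ANCOVA for eGFR, but no correlation is stated.

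**6. Composite (assumed rates only).** The plan gives no failure rate. If 0.9 were an arcsine difference, exact Fisher power for 16 against 16 is 55% to 58% over lower rates of 10% to 50%.

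**7. Non-inferiority (assumed rates only).** With equal true failure rates p and 16 per arm, SE = sqrt(2p(1 − p)/16), which is 0.106 at p = 0.1 and 0.177 at p = 0.5. The 95% half-width (1.96 × SE) is 21 to 35 points. The margin needed for 80% power at one-sided 0.025 (2.80 × SE) is 30 to 50 points.

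**The case against.** The sample size rests on the pilot rule, so no patient numbers depend on the power sentence. That stands. A reader might infer from step 2 that the trial should have 21 per arm; the documents do not support this, because 48 was never derived from 80% power.

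No section specifies an unadjusted two-arm comparison of means, and Section 10.5.2 adjusts eGFR for Month 1. So 69% depends on the reading and is not a proven miscalculation. That also stands. A reader might infer that a one-sided result was mislabelled as two-sided. The exact match suggests it, but the cited textbook is not available here and the plural arms in Section 3.2 leave room for pooling. No section specifies that pooling, however: the pooled safety set in Section 10.4 is all patients as one group. Nor does Section 10.4.2 settle the contrast, since it compares everolimus with tacrolimus and every arm starts on tacrolimus.

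A reader might also set 80% against the 56% power at 12 evaluable per arm and call it a 24-point overstatement. Section 10.6 claims power only at 16 per arm, so this does not hold. Nor should eGFR losses be overdrawn. Section 10.4.3 bars carrying values beyond 6 weeks, but keeps the last value before dialysis or re-transplantation after graft loss. Sections 6.5.8 and 7.5 keep most patients who stop study drug under follow-up for creatinine. Some loss is plausible; its size is not known.

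**Conclusion.** The point holds as an under-specified power statement that fails on its plainest reading. For two arms compared on a continuous endpoint, unadjusted, with all 16 per arm evaluable, power is 69% rather than 80%, a gap of 11 points, or 8 points by normal approximation. The readings that come close to 80% need either a one-sided test, which the text rules out, or a pooled contrast or baseline correlation that the plan does not state. The sentence gives no information on the primary composite. Even that composite's definition varies: the synopsis objective counts "treated Biopsy-Proven Acute Rejection (BPAR) episodes, delayed graft function, graft loss, and death or loss to follow-up", while Sections 3.1 and 10.4.1 leave out delayed graft function.

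The non-inferiority label is a separate defect. It names a conclusion that the plan has no rule to reach, and the 30 to 50 point margins above, which rest on assumed failure rates, show that 16 per arm could support only a very wide one.

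Both should be fixed. Neither shows that 48 is wrong for a pilot.

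**What to change.** Keep 48 patients, justified by the pilot rule. In Section 10.6 and the synopsis, replace the power sentence with one for a named continuous endpoint, for example: *For [endpoint], compared between two arms by an unadjusted two-sided 0.05 t-test, 16 per arm gives 80% power for a difference of 1.02 SD (1.20 SD if 12 per arm are evaluable). This does not apply to the composite efficacy failure rate.*

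If another basis was meant, state it with its assumption: for pooled everolimus arms, 0.88 SD at 32 against 16, or 1.02 SD at 24 against 12; for ANCOVA, the assumed correlation. Otherwise delete the sentence. Any illustration for the composite should be labelled as an assumption, and should wait until the sections that do and do not count delayed graft function are reconciled.

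In Section 4, remove the non-inferiority label and state that a non-significant difference will not be read as non-inferiority. A margin with a decision rule is the formal alternative, but at this size it would have to be very wide.

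Cost: wording only for the restatement and the label, with a less favourable detectable difference (1.02 SD instead of 0.9) and the loss of the non-inferiority claim. Writing a pooled contrast into Section 10.4.2 or 10.5.2 would be a new analysis, not only wording.
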